## **7.4 Analysis Populations**

ITT population, Per-Protocol (PP) population and Safety populations are three populations for statistical analysis. The ITT population and PP population are used in analysis of efficacy variables, and the safety population perform in analysis of safety variables.

### **7.4.1 Intent-to-Treat Population (ITT)**

The ITT population includes all randomized patients who meet all inclusion criteria and

**Protocol: GHLIP-2-001**

**Study Sponsor: Golden Biotechnology Corporation**

exclusion criteria, take at least one study medication and have at least one post-baseline measurement.

#### **7.4.2 Per Protocol Population**

The PP population is a subset of the ITT population and includes all randomized patients who complete 12 weeks of treatment without major protocol violation.

The definition of major protocol violations include

- violate the enrollment criteria,
- use of prohibited medications indicated to treat dyslipidemia,
- drug compliance less than 70%.

#### **7.4.3 Safety Population**

All subjects who received at least one study medication will be included in the safety analysis population.

### **7.5 Covariates and Subgroups**

The primary efficacy endpoint for assessing the superiority of Antroquinonol (50mg, 100mg, and 150mg) to placebo is the mean percentage reduction change of TG in patients with hyperlipidemia by using analysis of covariance (ANCOVA) model using baseline measurement as covariates, if the differences in baseline characteristics, such as gender, age, weight etc., are observed, for comparing the effectiveness between the treatment groups and placebo.

### **7.6 Derived and Computed Variables**

The following derived and computed variables have been initially identified. It is expected that

**Protocol: GHLIP-2-001**

**Study Sponsor: Golden Biotechnology Corporation**

additional variables will be required. The SAP will not be amended for additional variables that are not related to the primary endpoint or key secondary endpoints. An additional derived or computed variables will be identified and document in the SAS programs that create analysis files.

- Age (years) = (date of giving informed consent – date of birth)/365.25
- BMI (kg/m^2) = Weight (kg) / Height (m^2)
- Treatment Compliance (%) =  $\frac{\text{Quantity of total dispensed} - \text{Quantity of total returned}}{\text{Treatment period (84 days)}} \times 100\%$
- Percentage change from baseline of TG (%) =  $\frac{\text{Day85 (TG)} - \text{Day1 (TG)}}{\text{Day1 (TG)}} \times 100\%$

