4.5.2. Blinding procedures

After enrollment, subjects will be randomly assigned to receive one of the study treatments in a double-blind fashion. The identity of the treatments will be concealed. The placebo will be masked by the same appearance, odor and taste as the study drug (Antroquinonol). Subjects,

investigator, site staff, persons performing study assessments and data analysts will remain blind to the treatment assignment from the time of randomization until data lock.

All patients enrolled should take 3 capsules within 15 minutes after the first meal every day. In the study group, subjects will be treated with (1) 3* Antroquinonol 50 mg capsule; (2) 2* Antroquinonol 50 mg capsule and 1 capsule of placebo; (3) 1* Antroquinonol 50 mg capsule and 2 capsules of placebo and (4) in the control group, subjects will be treated with 3 capsules of placebo.

The blinding during the study is maintained by administration of matching placebo capsules to patients in the placebo group. Furthermore, the project teams of Golden Biotechnology Corporation and the CRO as well as the investigator and his/her study personnel will be blinded with respect to patients' assignment to one of the four treatment groups.

Treatment codes should not be broken except in the case of emergency situations. If the investigator wishes to know the identity of the treatment given to study patients for any other purpose, this request should first be discussed with Golden Biotechnology Corporation.

As per regulatory reporting requirement, Golden Biotechnology Corporation will unblind the identity of the study medication for all unexpected (as per the Investigator Brochure [IB]) serious adverse events that are considered by the investigator to be related to study drug. Details of patients who are unblinded during the study will be included in the Clinical Study Report.

All other individuals directly involved in this study will remain blinded until the final analysis of the primary parameter.

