9.3. Analyzed Population

There will be three populations in this study, Intent-To Treat (ITT) population, Per-Protocol (PP) population and Safety populations for statistical analysis. Primary efficacy analysis will be performed in both ITT and PP population, while secondary efficacy analyses will be performed in ITT population only. Safety population will be used in analysis of safety variables. The populations for analysis applied into this study are defined as following:

Intent to Treat Population (ITT):

The ITT population includes all randomized patients who meet all inclusion criteria and exclusion criteria, take at least one study medication and have at least one post-baseline

measurement.

Per-Protocol Population (PP):

The PP population is a subset of the ITT population and includes all randomized patients who complete 12 weeks of treatment without major protocol violation.

The definition of major protocol violations include (1) violate the enrollment criteria, (2) use prohibited medications indicated to treat dyslipidemia, and (3) drug compliance less than 70%.

Safety Analysis Population:

All subjects who received at least one study medication will be included in the safety analysis population.

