## **8.6 Treatment Compliance**

Patients will be instructed to take a total of three capsules of Antroquinonol and/or placebo in different combination once per day and return to the study site on the next visit. A record of the

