**Protocol: GHLIP-2-001**

**Study Sponsor: Golden Biotechnology Corporation**

number of capsules dispensed, taken and returned for each patient must be documented on the CRF. Compliance will be assessed from the information recorded in the CRF, including study medication count, start and end date of therapy. The treatment compliance rate will be determined by the number of taken drugs divided by number of taken drugs divided by number of days of treatment taken  $\times$  3 capsules per day that should be taken and presented in the percentage format, given by:

- Treatment Compliance (%) =  $\frac{\text{Quantity of total dispensed} - \text{Quantity of total returned}}{\text{Treatment period (84 days)}} \times 100\%$

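### The compliance formula printed in SAP 7.6 and 8.6 omits the three capsules per day, so as printed full adherence reads 300% and 59 of 252 capsules (23.4%) meets the 70% per-protocol criterion

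*SAP*

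**What the plan says.** Dosing is the same in every arm. Protocol 4.5.2 states: "All patients enrolled should take 3 capsules within 15 minutes after the first meal every day". SAP 8.6 agrees: "Patients will be instructed to take a total of three capsules of Antroquinonol and/or placebo in different combination once per day". SAP 8.6 also fixes the unit of the drug count, requiring that the "number of capsules dispensed, taken and returned for each patient must be documented on the" CRF.

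SAP 7.6 (the list of derived variables) and SAP 8.6 print the same formula: total dispensed minus total returned, over "Treatment period (84 days"), times 100%. Neither copy has a capsules-per-day multiplier.

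The sentence leading into the formula in SAP 8.6 describes something else. It gives the rate as the "number of taken drugs divided by number of taken drugs divided by number of days of treatment taken", multiplied by "3 capsules per day that should be taken and presented in the percentage format, given by", and the formula without the 3 follows directly.

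The result feeds the per-protocol definition. SAP 7.4.2 lists "drug compliance less than 70"% among three major violations, and Protocol 9.3 has the same item ("3) drug compliance less than 70"%). Compliance is also a safety endpoint (Protocol 3.4, SAP 3.2.3) and has its own planned table, 14.4.7.1.

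**The concern.** The numerator counts capsules and the denominator counts days, so the printed ratio is capsules per day and not a percentage of expected intake. The prose and the formula in SAP 8.6 cannot both be followed. In SAP 7.6, where a programmer would look for derivations, the formula stands without the prose, and nothing says which version governs. The prose cannot be used word for word either, because it divides by the number of drugs taken twice over. The two versions also differ on the day count: a fixed 84 days in the formula, days of treatment in the prose.

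The 70% criterion is at stake. It has no upper limit, so an inflated value never excludes anyone, and on the printed scale it stops testing 70% adherence. The per-protocol set serves the primary endpoint (Protocol 9.3; SAP Table 14.2.1.2), and the SAP also plans per-protocol tables for the secondary endpoints (14.2.2.2, 14.2.3.2) and subgroup analyses in that set (SAP 9.6). Table 14.4.7.1 would show about 300% for adherent completers.

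**Working it through.** The documents give no worked compliance value to reproduce. The one figure in the formula, 84 days, is consistent with the design: 12 weeks x 7 = 84, and Day 85 - Day 1 = 84.

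**Inputs**
- Capsules per day: 3 (Protocol 4.5.2, SAP 8.6)
- Treatment period: 84 days (SAP 7.6, 8.6)
- Cut-off: below 70% is a major violation (Protocol 9.3, SAP 7.4.2)
- Visit 5 window: Day 85 ± 3 (study schedule), taken here as 81 to 87 treatment days

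**Full adherence**
- Expected capsules: 3 x 84 = 252
- Printed formula: 252/84 = 300%
- With the factor of 3: 252/(3 x 84) = 100%

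**Fewest capsules that meet the 70% criterion**
- Printed formula: 0.70 x 84 = 58.8, so 59 pass (59/84 = 70.2%) and 58 fail (58/84 = 69.0%)
- True adherence at 59 capsules: 59/252 = 23.4%
- With the factor of 3: 0.70 x 252 = 176.4, so 177 are needed (177/252 = 70.2%; 176/252 = 69.8% fails)

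**Across the Visit 5 window**
- 81 days: 243 capsules expected; 59/243 = 24.3%; a true 70% needs 0.70 x 243 = 170.1, so 171
- 87 days: 261 capsules expected; 59/261 = 22.6%; a true 70% needs 0.70 x 261 = 182.7, so 183

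**Day count, with the factor of 3 in place**

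For completers, a fixed 84 days matters little: a fully adherent patient reads 243/252 = 96.4% at 81 days and 261/252 = 103.6% at 87 days. For early dropouts, who appear in the Safety Population table, it matters a good deal. For a fully adherent patient who stops early:

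| Stops after | Capsules taken | Printed formula | Fixed 84 days x 3 | Actual days x 3 |
|---|---|---|---|---|
| 28 days | 84 | 84/84 = 100% | 84/252 = 33.3% | 84/84 = 100% |
| 56 days | 168 | 168/84 = 200% | 168/252 = 66.7% | 168/168 = 100% |

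**The case against.** The strongest reply is that the intent is plain. SAP 8.6 is the section devoted to compliance, its prose names three capsules per day, and the repeated clause reads as a typing slip. Adherent patients would cluster near 300% in every arm, and the blinded data review (SAP 6.2) would probably expose that and allow correction from existing CRF counts. The 23.4% figure is also an outer bound. It concerns the compliance criterion alone: a per-protocol patient must also complete 12 weeks with no other major violation, entry excludes patients thought unreliable about medication, and those who cannot comply may be withdrawn.

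Much of this stands as a limit on the practical effect. It does not remove the contradiction. No section names compliance as an item for the blinded review, and a correction made there would leave the day count to be chosen at that point.

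Two alternative readings are weaker. The formula would work if quantity meant three-capsule daily doses, but SAP 8.6 counts capsules. A multiplier lost in converting the PDF cannot be wholly excluded, but both copies read as complete and identical.

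A fair point concerns the remedy. The text compels the factor of 3. Using actual days means choosing between two conflicting SAP statements, and it makes a patient who stops at day 28 read 100% where a fixed 84 days gives 33.3%.

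**Conclusion.** The formula is wrong as printed in both places and conflicts with the SAP's own prose. If it is programmed as it stands, compliance is inflated threefold and the 70% criterion acts as a 23.3% criterion (70%/3). Patients who complete 12 weeks with true adherence from about 23% to 70%, and no other major violation, would stay in the per-protocol set.

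This assumes that quantity means capsules, as SAP 8.6 indicates, and that the printed formula is what gets programmed. The documents give no adherence distribution, so the number of patients affected is unknown and could be zero. The ITT definition has no compliance criterion, so the ITT analysis is unaffected. The correction should be made, but it does not threaten the main result.

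**What to change.** In both SAP 7.6 and SAP 8.6, print:

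Compliance (%) = (capsules dispensed - capsules returned) / (3 x days on treatment) x 100

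Apply the 70% per-protocol cut-off to that value. In addition:
- Define quantity as capsules.
- Delete the repeated clause in the SAP 8.6 sentence.
- State that the denominator uses actual treatment days, as the SAP 8.6 prose implies, and define them, for example as first to last dose with missed days counted. Otherwise missed days could drop out of the denominator. If the sponsor prefers a fixed 84 x 3, it should say so in both sections.
- Note how early dropouts will read in Table 14.4.7.1 under the chosen rule.

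The cost is a one-line correction in two places and a sentence or two on the day count. No new data are needed, because capsule counts and therapy start and end dates are already on the CRF. It should be done before the blinded data review and database lock.

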### **3.2.3 Safety Endpoints**

1. Changes in laboratory examination including hematological, biochemical parameters, and urinary analysis.
2. Changes in electrocardiogram test, vital signs, and physical examinations.
3. Analysis of adverse events.
4. Compliance and tolerability of the study drug

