### 14.4 Safety Data

Table 14.4.1.1 Summary of Vital Sign by Visit (Safety Population)

Table 14.4.1.2 Summary of Mean Change from Baseline in Vital Sign (Safety Population)

Table 14.4.2.1 Summary of of Physical Examinations (Normal/Abnormal) (Safety Population)

Table 14.4.2.2 Transition Table of Physical Examinations (Safety Population)

Table 14.4.3.1 Summary of baPWV, ABI, E/E', and HU (Safety Population)

Table 14.4.3.2 Summary of of 12-Lead ECG, baPWV, ABI, E/E', and HU (Normal/Abnormal) (Safety Population)

Table 14.4.3.3 Transition Table of 12-Lead ECG, baPWV, ABI, E/E', and HU after 12 Weeks (Safety Population)

Table 14.4.4.1 Summary of Laboratory Assessment-Lipid Profile (Safety Population)

Table 14.4.4.2 Summary of Laboratory Assessment-Serum Chemistry (Safety Population)

Table 14.4.4.3 Summary of Laboratory Assessment-Hematology (Safety Population)

Table 14.4.4.4 Summary of Laboratory Assessment-Biomarkers (Safety Population)

Table 14.4.4.5 Summary of Laboratory Assessment-Urinary Exam (Safety Population)

Table 14.4.5.1 Summary of Laboratory Assessment-Lipid Profile (Normal/Abnormal) (Safety Population)

Table 14.4.5.2 Summary of Laboratory Assessment-Serum Chemistry (Normal/Abnormal) (Safety Population)

Table 14.4.5.3 Summary of Laboratory Assessment-Hematology (Normal/Abnormal) (Safety Population)

Table 14.4.5.4 Summary of Laboratory Assessment-Biomarkers (Normal/Abnormal) (Safety Population)

Table 14.4.5.5 Summary of Laboratory Assessment-Urinary Exam (Normal/Abnormal) (Safety Population)

Table 14.4.5.6 Summary of Laboratory Assessment-Microscopy (Normal/Abnormal) (Safety Population)

Table 14.4.6.1 Transition Table of Laboratory Assessment-Lipid Profile (Safety Population)

Table 14.4.6.2 Transition Table of Laboratory Assessment-Serum Chemistry (Safety Population)

Table 14.4.6.3 Transition Table of Laboratory Assessment-Hematology after 12 Weeks (Safety Population)

Table 14.4.6.4 Transition Table of Laboratory Assessment-Biomarkers after 12 Weeks (Safety Population)

Table 14.4.6.5 Transition Table of Laboratory Assessment-Urinary Exam after 12 Weeks (Safety Population)

Table 14.4.6.6 Transition Table of Laboratory Assessment-Microscopy after 12 Weeks (Safety Population)

Table 14.4.7.1 Summary of Subject Compliance for the Study Drugs (Safety Population)

Table 14.4.8.1 Summary of Adverse Events by Treatment Groups (Safety Population)

Table 14.4.8.2 Summary of Adverse Events by MedDRA Coding (Safety Population)

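### The compliance formula in SAP 7.6 and 8.6 divides capsules by a fixed 84 days, against the SAP 8.6 text, which divides by the patient's own treatment days times three capsules

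*SAP*

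**What the plan says.** SAP 7.6 (Derived and Computed Variables) defines treatment compliance as quantity dispensed minus quantity returned, divided by "Treatment period (84 days"), times 100%. SAP 8.6 (Treatment Compliance) prints the same formula.

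The text directly above the formula in SAP 8.6 describes something else. The capsules taken are "divided by number of days of treatment taken", multiplied by "3 capsules per day that should be taken and presented in the percentage format". (The sentence also repeats its numerator phrase, apparently a slip.) The data to be used are those on the CRF, "including study medication count, start and end date of therapy". The unit is the capsule: the "number of capsules dispensed, taken and returned for each patient must be documented on the" CRF.

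The result is used in two places:

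- "Compliance and tolerability of the study drug" is a safety endpoint in SAP 3.2.3 and is tabulated in "Table 14.4.7.1 Summary of Subject Compliance for the Study Drugs (Safety Population"). That population contains everyone who took any study medication (SAP 7.4.3), so it includes all early stoppers.
- Compliance below 70% is a major protocol violation that removes a patient from the per-protocol population (protocol 9.3, SAP 7.4.2). That population also requires completion of 12 weeks of treatment.

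**The concern.** The two rules in SAP 8.6 cannot both be programmed. They differ by a factor of three for everyone, and they differ again for any patient not treated for exactly 84 days.

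The missing factor is easy to notice, because completers would score near 300%. The obvious repair is to write 3 × 84 = 252 in the denominator. That makes completers look right and leaves the second fault in place: for a patient who stopped early, the denominator still counts days on which no capsules were due. A patient who took every capsule until stopping would be shown as a poor complier.

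What is at stake is how the compliance table reads. The protocol allows several routes to early stopping: withdrawal for toxicity with no dose modification (5.3), for adverse effects or lack of response (4.5.4), and of non-responders (4.4). If stopping differed between arms, the table would show different compliance even with identical adherence on drug.

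**Working it through.** **Inputs.** Treatment period 84 days (SAP 7.6); this agrees with 12 × 7 = 84 and with Day 85 − Day 1 = 84 in the visit schedule. Three capsules a day in every arm (protocol 4.5.2, SAP 8.6). Visit 5 window ±3 days (protocol 6.1). Per-protocol cut-off 70% (SAP 7.4.2). Planned dropout 20% overall (protocol 9.2).

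**Step 1. A fully adherent patient who stops after d days** has taken 3d capsules. The three candidate denominators give:

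| Days on drug (d) | Capsules | As printed: 3d/84 | Factor 3 only: 3d/252 | 8.6 text: 3d/(3 × d) |
|---|---|---|---|---|
| 14 | 42 | 50% | 16.7% | 100% |
| 28 | 84 | 100% | 33.3% | 100% |
| 56 | 168 | 200% | 66.7% | 100% |
| 84 | 252 | 300% | 100% | 100% |

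Changing only the days and leaving out the factor of three would give 3d/d = 300% in every row, so the two corrections must be made together.

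**Step 2. The 70% rule as printed.** 0.70 × 84 = 58.8, so 59 capsules are enough. For a completer that is 59/252 = 23.4% of the capsules due. As printed, the rule excludes almost nobody.

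**Step 3. Arm mean with the factor of three restored but 84 days kept.** With dropout p, mean stop day m and full adherence on drug, the mean is (1 − p) + p × m/84.

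- Planned p = 0.20, stop times uniform over 84 days (assumption, m = 42): 0.80 + 0.20 × 0.5 = 90%. The 8.6 text gives 100%.
- Range over assumed p of 10% to 30% and m of 14 to 56: lowest 0.70 + 0.30 × 14/84 = 75.0%; highest 0.90 + 0.10 × 56/84 = 96.7%.

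**Step 4. Completers inside the Visit 5 window, factor of three restored.** The cut-off is 0.70 × 252 = 176.4 capsules.

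- Visit 5 on Day 82: 81 days, 243 capsules due; 176.4/243 = 72.6% true adherence.
- Visit 5 on Day 88: 87 days, 261 capsules due; 176.4/261 = 67.6%.
- A patient taking 58 full days out of 81 (71.6%) scores 174/252 = 69.0% and is excluded. One taking 59 out of 87 (67.8%) scores 177/252 = 70.2% and is kept.

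The shift is at most 2.6 percentage points and touches only completers whose true adherence lies between 67.6% and 72.6%. The documents do not indicate how many there would be.

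**The case against.** The best defence is that percent of planned dose taken is a legitimate descriptive measure, and a fixed 84 days (with the factor of three) delivers it. It does not hold here, because SAP 8.6 itself defines the other measure in words and names the therapy dates needed to compute it.

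Several other points stand, in whole or in part:

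- **One correction cures both faults.** The missing factor of three and the fixed period come from the same formula contradicting the same sentence. The factor of three is the larger error, since it affects every patient.
- **Early stopping is visible elsewhere.** Disposition and reasons for discontinuation (Tables 14.1.1.1 and 14.1.1.2) and adverse events leading to withdrawal by treatment group (SAP 10.1.2) are reported. No between-arm test of compliance is specified. The harm is confined to how one safety table reads.
- **Own-days compliance has a weak spot.** If the denominator ends at a self-reported last dose, a patient who silently stops capsules but keeps attending would score 100%. The end-of-therapy date on the CRF should therefore be used. For patients lost to follow-up, that date or the returned count may be missing.

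A reader might infer that the compliance table would mostly reflect dropout by dose, given the gastrointestinal reactions listed in protocol 8.2. The documents do not support that. They give one overall dropout figure and none by arm, and those reaction rates are not tied to dose or to withdrawal. With 20% dropout and the same stop times in every arm, all arms fall by the same amount.

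**Conclusion.** The formula in SAP 7.6 and 8.6 is wrong as written and contradicts the SAP 8.6 text. Taken literally it gives 300% for a perfect completer and nearly disables the 70% per-protocol rule. If only the factor of three is repaired, fully adherent early stoppers read d/84, and an arm at the planned 20% dropout reads about 90% instead of 100%. That last figure assumes full adherence on drug and uniform stop times; under the other assumptions shown it lies between 75.0% and 96.7%.

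Two limits apply. The 16.7% to 66.7% values are not what the printed formula yields; they hold only once 252 is in the denominator. Nor do early stoppers lose per-protocol status through this formula, since that population already requires 12 completed weeks. For completers, the effect of the fixed period on the 70% cut-off is small.

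The ITT analysis of triglycerides is unaffected. The correction should still be made before database lock, because compliance is a named safety endpoint and the 70% rule defines one of the two populations for the primary analysis.

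**What to change.** In SAP 7.6 and 8.6, replace both formulas in one change so that they match the 8.6 text:

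Compliance (%) = (capsules dispensed − capsules returned) / (3 × days from start to end of therapy as recorded on the CRF) × 100.

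State how the days are counted, so that dosing from Day 1 through Day 84 gives 84, and remove the repeated phrase in the 8.6 sentence. State also how a missing end date or unreturned supply is handled. Use this value for the 70% rule and for Table 14.4.7.1, and add treatment duration by arm to that table as a separate line.

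The cost is one formula, its program and one table line; SAP 8.6 already lists the inputs as CRF data. The small downside is that compliance no longer reflects early stopping, which the duration line and the disposition tables show instead.
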